4.3 Disposition of Subjects

The numbers of subjects enrolled, treated, discontinued from treatment (by reason), and replaced will be presented by dose cohort, including the expansion cohorts.

Note that subjects in the dose finding Phase 1 will be replaced if they do not experience a dose-limiting toxicity (DLT) and either of the following conditions hold:

- They do not receive all infusions of both IMPs in Cycle 1 within 28 days at the doses assigned to the cohort in which they are enrolled.
- They do not complete the safety follow-up through the end of the DLT evaluation period (14 days after the last dose of IMP in Cycle 1).

Subjects enrolled in the expansion cohorts may be replaced for these same reasons, at the discretion of the Sponsor.

4.4 Data Sets Analyzed

The following analysis sets will be used in the study:

- **Safety Analysis Set:** Includes all subjects who received at least one dose of IMP (even a partial dose).
- **Efficacy Analysis Set:** Includes all subjects who receive combination therapy in Cycle 1 Day 1.
- **Pharmacokinetic Analysis Set:** Includes all subjects who provide at least one post-dose concentration measurement.
- **Pharmacodynamic Analysis Set:** Includes all subjects who provide at least one post-dose sample.
- **ADA Analysis Set:** The ADA analysis set for mogamulizumab will include all subjects that have both a baseline subject ADA status and at least one on-treatment subject ADA status.

The number of subjects in the Safety Analysis, Efficacy Analysis, Pharmacokinetic Analysis, Pharmacodynamics Analysis Set, and ADA analysis set will be summarized.

4.5 Protocol Deviations

Protocol deviations (PDs) will be identified, logged, and reviewed during the course of the study. A determination of major versus minor PDs will be made according to the criteria outlined in the study protocol deviation review plan. A listing of all PDs will be provided. For purposes of CSR reporting, all important/major protocol deviations will be identified based on the following minimum criteria:

- Subjects who entered the study even though they did not satisfy the entry criteria
- Subjects who developed withdrawal criteria during the study but were not withdrawn
- Subjects who received the wrong treatment or incorrect dose

- Subjects who received an excluded concomitant treatment.

4.6 Demographic and Other Baseline Characteristics

Demographic and baseline characteristics will be summarized descriptively for both the Safety Analysis Set and the Efficacy Analysis Set. Gender, race, ethnicity, tobacco use, and baseline Eastern Cooperative Oncology Group (ECOG) performance status (PS) will be summarized with number and percentage presented for each category. Age, height, and weight at baseline will be described with summary statistics (n, mean, Std Dev, median, minimum, and maximum).

In addition, subject cancer history will be summarized descriptively. The characteristics include:

- Primary tumor type;
- Time from initial diagnosis of tumor to first dose day (in months);
- Time from locally advanced/metastatic disease to first dose day (in months);
- Stage at enrollment (locally advanced, metastatic);
- Metastatic sites (if applicable);
- EGFR mutation (positive, negative, other, not done), ALK rearrangement (positive, negative, other, not done), HPV infection (positive, negative, unequivocal, other, not done) and MSI (type of assay, PCR: MSI-high, MSI-low, MSI-stable, other, not done; IHC: positive, negative, other, not done); Oncogene assessment: KRAS, ROS1, BRAF,...etc.

4.6.1 Medical History

Medical history data will be presented in data listings for individual subjects.

4.7 Prior/Concomitant Cancer and Non-Cancer Therapies/Procedures

4.7.1 Prior Cancer Therapy

The number of cancer therapy regimens that subjects received prior to enrollment will be summarized by frequency counts. The best response to the most recent line of therapy will be provided. This will be performed on the Safety Analysis Set.

4.7.2 Prior Cancer Surgery, Radiation Therapy, and Other Therapy

The number and percentage of subjects who underwent prior cancer surgery, radiation therapy, and other types of cancer therapy will be summarized separately for each of these categories. This will be performed on the Safety Analysis Set.

4.7.3 Post Treatment Cancer Therapy

The number and percentage of subjects who received any post-treatment cancer therapy will be summarized for the Safety Analysis Set.

4.7.4 Other Prior/Concomitant Medications

Prior and concomitant medications will be coded using the World Health Organization (WHO) Drug Dictionary (version September 2015). Prior medications include medications that were taken within 30 days prior to the first dose of IMP. Concomitant medications during the treatment period include medications that started at any time and were taken at any time after the start of IMP until 30 days after the last dose of IMP.

The number and percentage of subjects taking prior medications or concomitant medications during the treatment period will be summarized by anatomical therapeutic chemical (ATC) and preferred term (PT) for the Safety Analysis Set. If a subject takes more than one medication in the same ATC class, the subject will be counted only once within that classification. The same subject may contribute to two or more preferred terms within the same ATC classification.

4.8 Study Drug Exposure and Compliance

The maximum number of cycles initiated, cycles that a subject initiated, extent of exposure (defined as Last Dose Date – First Dose Date + 1), and the number of infusions administered (mogamulizumab: Days 1, 8, 15, 22 of the first cycle and Days 1 and 15 of each subsequent cycle; nivolumab: Days 1 and 15 of each cycle) per subject will be summarized for each medication. Infusion time (in minutes) per administration (overall, at 1st – 4th infusion, and later for mogamulizumab; at 1st and 2nd infusions, and later for nivolumab) will also be presented. These parameters will be summarized for the Safety Analysis Set.

Cumulative dose statistics will be calculated for mogamulizumab as follows.

- Cumulative actual dose (mg/kg): Sum of {Actual dose administered (mg)/Body weight (kg)};
- Cumulative assigned dose (mg/kg): Sum of {Planned dose (mg/kg)};
- Relative dose intensity (%):

$$\frac{\text{Number of doses administered in Cycle 1} + \text{Number of doses administered in Subsequent Cycles} \times 2}{[(\text{Number of cycles initiated}) \times 4]} \times \frac{\text{Number of cycle initiated} \times 28}{\text{Last dose date} + n^* - \text{First dose date}} \times 100$$

where $n^* = 7$ when the patient was only treated for 1 cycle, otherwise, $n^* = 14$.

Note that body weight for each infusion is defined as weight entered at the visit for calculation of the dose level.

Similarly, cumulative actual dose (mg), cumulative assigned dose (mg), and relative dose intensity (%) will be calculated for nivolumab as well. Note that the assigned dose for nivolumab is 240 mg per administration.

- Cumulative actual dose (mg): Sum of {Actual dose administered (mg)};
- Cumulative assigned dose (mg): Sum of {Planned dose (mg)} = (Last nivolumab dose date – First nivolumab dose date) × 240/14;
- Relative dose intensity (%): Cumulative actual dose/Cumulative assigned dose × 100.

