**Table 8.1.1-1 Dosing Schedules of Mogamulizumab and Nivolumab During Phase 1 and Phase 2**

	Cycle 1				Cycle $\geq$ 2	
	Day 1	Day 8	Day 15	Day 22	Day 1	Day 15
Nivolumab	X		X		X	X
Mogamulizumab	X	X	X	X	X	X

Treatments will be administered on an outpatient basis. Each dose of IMP will be prepared by the pharmacy (refer to the Pharmacy Manual for full preparation, administration, and storage requirements). Mogamulizumab dosing calculations should be based on the body weight assessed at Cycle 1 Day 1 (baseline). Mogamulizumab dose adjustments for each cycle are required for greater than a 10% change in body weight.

All subjects will receive 240 mg of nivolumab as at least a 30-minute iv infusion on Days 1 and 15 of each 28-day cycle. When both nivolumab and mogamulizumab are administered at the same visit, the infusion of mogamulizumab will be started at least 30 minutes after the end of infusion of nivolumab.

- Nivolumab injection is to be administered as an iv infusion through a 0.2-micron to 1.2-micron pore size, low-protein binding polyethersulfone membrane in-line filter
- Subjects may be dosed no less than 12 days from the previous dose of nivolumab.
- There are no premedications recommended for nivolumab prior to the first infusion.

- Subjects should be carefully monitored for infusion-related reactions during IMP administration. If an acute infusion-related reaction is noted, subjects should be managed according to Section 8.2.2.

Subjects will then receive the cohort-assigned dose of mogamulizumab as at least a 1-hour iv infusion on Days 1, 8, 15, and 22 of the first cycle and on Days 1 and 15 of subsequent cycles.

- Mogamulizumab injection dose is to be administered as an iv infusion through a 0.22- or 0.2- $\mu$ m in-line filter.
- Subjects may be dosed no less than 5 days from the previous dose of mogamulizumab.
- Premedication with acetaminophen orally and diphenhydramine 50 mg iv (or equivalent) is recommended before the *first* mogamulizumab infusion (see Section 8.2.1).
- Subjects should be carefully monitored for infusion-related reactions during IMP administration. If an acute infusion-related reaction is noted, subjects should be managed according to Section 8.2.2.

Subjects should be closely monitored for AEs for at least:

- 30 minutes after the completion of the nivolumab infusion;
- 4 hours after the completion of the mogamulizumab infusion for the first 2 combination infusions (i.e., Cycle 1, Days 1 and 15); and

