Add footnote "Medications with start dates within 30 days of the first dose date of the study treatment, and ended prior to the first dose date of the study treatment are presented.".]

Table 14.1.2.6.4
Summary of Concomitant Steroids and Immune Modulating Medications by Route of Administration
Safety Analysis Set

[Note: Use Systemic Use, Topical. Defined as
Systemic = (Oral, Intravenous, Injection, Intrahepatic, Nasogastric, Intramuscular, Intrapleural, INTRAMUSCULAR, Subcutaneous, Epidural)
Topical = (Topical, Intraocular, Nasal, Respiratory, Rectal, Vaginal, Transdermal, Sublingual). Add footnote: Medications that started at any time until 30 days after the last dose date, and were taken at any time after the first dose date are presented.]]

Table 14.1.3.1.1
 Summary of Extent of Exposure to Mogamulizumab
 Subjects in Phase 1 (Dose Finding)

	Mogamulizumab 1 mg/kg + Nivolumab 240 mg N=xxx
Number of Cycles per Subject	
n	xx
Mean	xx.x
Std Dev	xx.xx
Median	xx.x
Minimum	xx
Maximum	xx
Cycle Initiated (n, %)	
Cycle 1 Day 1	xx (xx.x)
Cycle 1 Day 8	xx (xx.x)
Cycle 1 Day 15	xx (xx.x)
Cycle 1 Day 22	xx (xx.x)
Cycle 2 Day 1	xx (xx.x)
Cycle 2 Day 15	xx (xx.x)
...	xx (xx.x)
Maximum Cycle Initiated (n, %)	
1	xx (xx.x)
2	xx (xx.x)
3	xx (xx.x)
...	
Number of Infusions	
n	xx
Total [1]	xxx
Mean	xx.x
Std Dev	xx.xx
Median	xx.x
Minimum	xx
Maximum	xx

[1] Total number of infusions among all subjects in the treatment group.

[2] Last dose infusion - First dose infusion + 1

[3] $\{[(\text{Number of doses administered in cycle 1} + (\text{Number of doses administered post cycle 1} \times 2))/(\text{Number of cycles initiated} \times 4)]$
 $\times [\text{Number of initiated cycles} \times 28/((\text{Last dose date} + n^*) - \text{First dose date})]\} \times 100$, where $n^* = 7$ when the patient was only
treated for 1 cycle, otherwise, $n^* = 14$.

Table 14.1.3.1.1
 Summary of Extent of Exposure to Mogamulizumab
 Subjects in Phase 1 (Dose Finding)

	Mogamulizumab 1 mg/kg + Nivolumab 240 mg N=xxx
Extent of Exposure (days) [2]	
n	xx
Mean	xx.x
Std Dev	xx.xx
Median	xx.x
Minimum	xx
Maximum	xx
Cumulative Actual Dose (mg/kg)	
n	xx
Mean	xx.x
Std Dev	xx.xx
Median	xx.x
Minimum	xx
Maximum	xx
Cumulative Assigned Dose (mg/kg)	
n	xx
Mean	xx.x
Std Dev	xx.xx
Median	xx.x
Minimum	xx
Maximum	xx
Relative Dose Intensity (%) [3]	
n	xx
Mean	xx.x
Std Dev	xx.xx
Median	xx.x
Minimum	xx
Maximum	xx
Number of Patients with Dose Intensity of	
<70%	xx (xx.x)
>=70% - <90%	xx (xx.x)

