	Mogamulizumab 1 mg/kg + Nivolumab 240 mg N=xxx
>=90% - <110%	xx (xx.x)
>=110%	xx (xx.x)

[1] Total number of infusions among all subjects in the treatment group.

[2] Last dose infusion - First dose infusion + 1

[3] $\{ \text{Number of doses administered} / [(\text{Number of cycles initiated} - 1) \times 2 + 4] \times [\text{Number of initiated cycles} \times 28 / [(\text{Last dose date} + n^*) - \text{First dose date}]] \} \times 100$, where $n^* = 7$ when the patient was only treated for 1 cycle, otherwise, $n^* = 14$.

Same template will be used for the following table for Phase 2 subjects:

Table 14.1.3.1.2
Summary of Extent of Exposure to Mogamulizumab
Subjects in Phase 2 (Cohort Expansion)

Programming note: First page of the table is for "All Cancer Types". Subsequent pages are for NSCLC SQ, NSCLC NSQ PD-L1 non-expressing, Ovarian, CRC, SCCHN, HCC, Pancreatic cancer types separately. Only the MTD group will be presented.

Table 14.1.3.2.1
Summary of Extent of Exposure to Nivolumab
Subjects in Phase 1 (Dose Finding)

		Mogamulizumab 1 mg/kg + Nivolumab 240 mg N=xxx
Number of Cycles per Subject	xx	
n	xx.x	
Mean	xx.xx	
Std Dev	xx.x	
Median	xx	
Minimum	xx	
Maximum		
Cycle Initiated (n, %)		xx (xx.x)
Cycle 1 Day 1		xx (xx.x)
Cycle 1 Day 15		xx (xx.x)
Cycle 2 Day 1		xx (xx.x)
Cycle 2 Day 15		xx (xx.x)
...		xx (xx.x)
Maximum Cycle Initiated (n, %)		xx (xx.x)
1		
2		xx (xx.x)
3		xx (xx.x)
...		xx (xx.x)
Number of Infusions		
n		
Total [1]	xx	
Mean	xx.x	
Std Dev	xx.xx	
Median	xx.x	
Minimum	xx	
Maximum	xx	

[1] Total number of infusions among all subjects in the treatment group.

[2] Last dose infusion - First dose infusion + 1

[3] Cumulative dose (mg) / Cumulative assigned dose (mg) x 100, where cumulative assigned dose = (Last nivolumab dose date - First nivolumab dose date) x 240/14

Table 14.1.3.2.1
 Summary of Extent of Exposure to Nivolumab
 Subjects in Phase 1 (Dose Finding)

	Mogamulizumab 1 mg/kg + Nivolumab 240 mg N=xxx
Extent of Exposure (days) [2]	xx
N	xx.x
Mean	xx.xx
Std Dev	xx.x
Median	xx
Minimum	xx
Maximum	
Cumulative Actual Dose (mg)	xx
N	xx.x
Mean	xx.xx
Std Dev	xx.x
Median	xx
Minimum	xx
Maximum	
Cumulative Assigned Dose (mg)	xx
n	xx.x
Mean	xx.xx
Std Dev	xx.x
Median	xx
Minimum	xx
Maximum	
Relative Dose Intensity (%) [3]	xx
n	xx.x
Mean	xx.xx
Std Dev	xx.x
Median	xx
Minimum	xx
Maximum	

[1] Total number of infusions among all subjects in the treatment group.

[2] Last dose infusion - First dose infusion + 1

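### The nivolumab relative dose intensity formula drops the last 14-day interval, so full dosing reads above 100% and one-dose subjects divide by zero; mogamulizumab has two conflicting formulas

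*SAP*

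**What the plan says.** **Nivolumab.** SAP Section 4.8 defines the numerator as "Cumulative actual dose (mg): Sum of {Actual dose administered (mg)}", the ratio as "Relative dose intensity (%): Cumulative actual dose/Cumulative assigned dose × 100", and the assigned dose as the sum of planned doses, which the same line equates with ("Last nivolumab dose date – First nivolumab dose date) × 240/14". It adds: "Note that the assigned dose for nivolumab is 240 mg per administration". Footnote [3] of the Table 14.1.3.2.1 shell repeats the rule: "where cumulative assigned dose = (Last nivolumab dose date - First nivolumab dose date) x 240/14". The Phase 2 table, 14.1.3.2.2, uses the same template. The schedule comes from Protocol Section 8.1.1: "All subjects will receive 240 mg of nivolumab as at least a 30-minute iv infusion on Days 1 and 15 of each 28-day cycle".

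**Mogamulizumab.** Section 4.8 gives an RDI formula that counts each dose after Cycle 1 twice, divides by 4 × cycles initiated, and scales by 28 × cycles over the dosing span. The span is extended past the last dose by n* days: 7 if only one cycle was given, otherwise 14. The Table 14.1.3.1.1 shell runs over two parts, each with a footnote [3]. The first matches Section 4.8. The second, beneath the part that shows the RDI row and its categories, divides the unweighted dose count by (cycles − 1) × 2 + 4, with the same time scaling.

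Exposure is summarized for the Safety Analysis Set, which SAP Section 4.4 defines to include anyone who received even a partial dose.

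**The concern.** Measuring from first dose to last dose counts the intervals between doses, which is one fewer than the number of doses. The nivolumab numerator counts every dose, so numerator and denominator do not cover the same period. Section 4.8 introduces the nivolumab statistics as analogous to the mogamulizumab ones, yet only mogamulizumab gets an interval after the last dose.

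The protocol allows no intra-patient dose reduction (Section 8.1.2.1) and relies on delays (Section 8.1.2.2). RDI is the one summary statistic meant to show delays and omissions relative to plan, and a denominator that is one dose too small cancels exactly one of them. The distortion is largest in subjects who stop early. One-dose subjects are foreseeable, because Section 8.1.4 requires permanent discontinuation after a Grade 3 or higher infusion-related reaction. They have no RDI at all.

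For mogamulizumab, a programmer working from the shell can implement either formula, and the two can place the same subject in different printed categories.

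**Working it through.** The documents state no numerical RDI to reproduce. What can be tested is the SAP's own equation that the sum of planned nivolumab doses equals (last − first) × 240/14.

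**Inputs.** 240 mg per administration and the RDI definitions (SAP 4.8); one dose every 14 days (Protocol 8.1.1); up to 96 weeks of treatment, hence at most 48 doses (Protocol 6.3); mogamulizumab on Days 1, 8, 15, 22 of Cycle 1, then Days 1 and 15 (SAP 4.8).

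**Nivolumab, k full doses exactly on schedule**

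- Sum of planned doses: 240k mg.
- SAP formula: 14(k−1) × 240/14 = 240(k−1) mg. The equation fails for every k.
- RDI = 240k / 240(k−1) = k/(k−1).
- With 14 days added: (14(k−1) + 14) × 240/14 = 240k, so RDI = 100% for every k ≥ 1.

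| Doses given | Actual (mg) | Assigned by SAP (mg) | RDI by SAP | RDI with +14 days |
|---|---|---|---|---|
| 1 | 240 | 0 | undefined | 100% |
| 2 | 480 | 240 | 200% | 100% |
| 3 | 720 | 480 | 150% | 100% |
| 4 | 960 | 720 | 133.3% | 100% |
| 6 | 1440 | 1200 | 120% | 100% |
| 12 | 2880 | 2640 | 109.1% | 100% |
| 24 | 5760 | 5520 | 104.3% | 100% |
| 48 | 11520 | 11280 | 102.1% | 100% |

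**Nivolumab, one mid-course dose missed**

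| Given / scheduled | Span (days) | RDI by SAP | RDI with +14 days |
|---|---|---|---|
| 2 / 3 | 28 | 480/480 = 100% | 480/720 = 66.7% |
| 3 / 4 | 42 | 720/720 = 100% | 720/960 = 75% |
| 5 / 6 | 70 | 1200/1200 = 100% | 1200/1440 = 83.3% |

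**Same subject, both drugs.** One fully dosed cycle, then stop: mogamulizumab 4/4 × 28/(21+7) = 100%; nivolumab 2/1 = 200%.

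**Mogamulizumab.** With c cycles initiated, n₁ doses in Cycle 1 and n₂ later doses:

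- Formula A (Section 4.8 and the first footnote): (n₁ + 2n₂)/(4c) × 28c/(last − first + n*)
- Formula B (second footnote): (n₁ + n₂)/(2(c−1) + 4) × 28c/(last − first + n*)

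| Dosing history | A | B |
|---|---|---|
| One, two or six complete cycles | 100% | 100% |
| All given, stop after Cycle 2 Day 1 | 6/8 × 56/42 = 100% | 5/6 × 56/42 = 111.1% |
| All given, stop after Cycle 3 Day 1 | 10/12 × 84/70 = 100% | 7/8 × 84/70 = 105% |
| Two cycles, Cycle 1 Day 8 missed | 7/8 = 87.5% | 5/6 = 83.3% |
| Two cycles, Cycle 1 Days 8 and 22 missed | 6/8 = 75% | 4/6 = 66.7% |
| Two cycles, Cycle 2 Day 1 missed | 6/8 = 75% | 5/6 = 83.3% |

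The shell's categories are cut at 70%, 90% and 110%. The second and fifth rows change category.

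**The case against.** The arithmetic cannot be disputed, and neither redaction nor PDF reading explains it. The case on the other side concerns weight.

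- **Only the RDI row and the assigned dose that feeds it are wrong.** The same nivolumab table shows infusions, cycles, counts by dosing day, extent of exposure and cumulative actual dose. Listing 16.2.5.2 gives each infusion's date, delay and reason. A missed dose can be found elsewhere. This stands: missed doses are hidden in the RDI, not in the report as a whole.
- **One-dose subjects lose only their RDI.** They stay in the other rows, and the RDI row carries its own n. This also stands, although no rule says how to handle them.
- **The 100% reading needs a mid-course miss.** If the sixth of six doses is the one missed, the SAP formula gives 1200/960 = 125% and the corrected one 1200/1200 = 100%. No formula that ends at the last dose given can show a dropped final dose. This is true, and it limits the remedy as well.
- **RDI is not an endpoint and drives no decision.** The primary endpoints are adverse events, examinations, vital signs, ECGs and laboratory results. RDI helps a reader interpret tolerability, but the link to the primary objective is indirect.
- **The mogamulizumab conflict is a footnote mismatch.** Section 4.8 already states one formula, and the two versions agree for one-cycle subjects and for complete, fully dosed cycles. That makes it a smaller matter, but the conflicting version is printed under the RDI row, where a programmer will look.

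These points reduce the consequences. They do not make either formula right.

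**Conclusion.** The concern holds. As written, nivolumab RDI overstates on-schedule full dosing by the factor k/(k−1): twofold at 2 doses, 20% too high at 6, 2% at 48, and undefined at 1. It also cancels exactly one missed mid-course dose or 14-day delay. The two mogamulizumab formulas in the Table 14.1.3.1.1 shell conflict whenever a subject with two or more cycles stops mid-cycle, or misses a dose as in the histories shown, and the difference can cross a printed cut-point.

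These figures assume full 240 mg doses exactly 14 days apart; visit windows would shift them slightly. They are per-subject values. The documents give no distribution of doses received, so the effect on the reported mean or median RDI cannot be computed. The effect is limited to descriptive exposure reporting; efficacy, dose finding and sample size are unaffected. The plan should be corrected before the tables are produced.

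**What to change.** 1. In SAP Section 4.8 and in the footnotes of Tables 14.1.3.2.1 and 14.1.3.2.2, define cumulative assigned nivolumab dose as (last nivolumab dose date − first nivolumab dose date + 14) × 240/14. This restores agreement with the sum of planned doses, treats the two drugs alike, and gives one-dose subjects a defined value without a special rule.
2. In Tables 14.1.3.1.1 and 14.1.3.1.2, delete the second version of footnote [3] so that only the Section 4.8 mogamulizumab formula remains.
3. Make sure Listing 16.2.5.3, which prints assigned dose, actual dose and RDI, uses the same definitions.

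The cost is a small SAP text change, edited footnotes and about one line of programming. No dosing rule or data collection changes. Reported nivolumab dose intensity will be lower, and it will still not show doses omitted after the last one given.

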4.9 Efficacy Analysis

The efficacy analysis is based on disease response assessments. Assessment of disease response will be performed by investigators using both the RECIST v1.1 and the irRECIST v1.1. Responses for each disease evaluation assessment will be recorded in eCRFs.

4.9.1 Analysis of Efficacy Variables

Tumor response is determined by the investigator at each timepoint when tumor imaging is performed. All response-related endpoints (BOR, TTR, DOR, and PFS) will be based on RECIST v1.1 and derived programmatically using the investigator's assessments of tumor response at each timepoint. In addition, BOR of CR/PR will be assessed using irRECIST v1.1 criteria. The date of response is based on the image dates. In the event that there are images taken on different days, the latest date among all images taken will be used for the response date if the overall response is non-PD. If the overall response is PD, then the earliest date of all images taken will be used for the progression date.

All analyses will be conducted for the Efficacy Analysis Set.

Best Overall Response (BOR)

The number and percentage of subjects in each BOR category (i.e., CR, PR, SD, PD, and inevaluable) will be summarized. Subjects who do not meet CR/PR will be classified as stable disease if assessed as SD (or better) at least 9 weeks after first dose of IMP. The percentage of subjects with BORs of either CR or PR, taking into account any requirement for confirmation, will be calculated. The rates will be presented along with two-sided 95% exact confidence intervals. The 95% CIs will be derived using the Clopper-Pearson (Hollander, 1973) exact binomial confidence interval method.

The following Table 2 describes the derivation of BOR from overall response assessments at each visit. Note that BOR categories referenced in this table can be based on RECIST v1.1 or irRECIST v1.1 overall responses. For RECIST v1.1, BOR will be derived based on both

definitions as described in Section 4, secondary endpoints. For irRECIST v1.1 overall response, the analysis focuses on whether the subjects were responding (i.e., CR or PR) or not (i.e., not CR/PR).

Table 2 Best Overall Response When Confirmation of Complete Response and Partial Response is Required

Overall Response First Timepoint	Overall Response Subsequent Timepoint	Best Overall Response
CR	CR	CR
CR	PR	SD, PD or PR ^a
CR	SD	SD provided minimum criteria for SD duration was met, otherwise, PD
CR	PD	SD provided minimum criteria for SD duration was met, otherwise, PD
CR	NE	SD provided minimum criteria for SD duration was met, otherwise, NE
PR	CR	PR
PR	PR	PR
PR	SD	SD
PR	PD	SD provided minimum criteria for SD duration was met, otherwise, PD
PR	NE	SD provided minimum criteria for SD duration was met, otherwise, NE
NE	NE	NE

a: If a CR is truly met at first time point, then any disease seen at a subsequent time point, even disease meeting PR criteria relative to baseline, makes the disease PD at that point (since disease must have reappeared after CR). Best response would depend on whether minimum duration for SD was met. However, sometimes ‘CR’ may be claimed when subsequent scans suggest small lesions were likely still present and in fact the patient had PR, not CR at the first time point. Under these circumstances, the original CR should be changed to PR and the best response is PR.

CR=complete response; NE=not evaluable; PD=progressive disease; PR=partial response; SD=stable disease.

Time to Response (TTR)

Time to response will only be summarized descriptively for responders (i.e., CR or PR).

Duration of Response (DOR)

Duration of response will be calculated from the first date of confirmed CR/PR to the date of death or the date of first documented tumor progression (PD), whichever is earlier, using RECIST v1.1. Subjects who remain alive and do not progress will be censored on the date of their last tumor assessment. Subjects who start subsequent therapy without a prior PD will be censored at the last tumor assessment prior to initiation of the subsequent anticancer therapy. Response duration will only be evaluated in subjects with a BOR of CR or PR.

The median DOR, along with its two-sided 95% CI (Brookmeyer, 1982), will be estimated using the Kaplan-Meier (KM) method.

Progression-Free Survival (PFS)

PFS will be calculated as the number of days from the first dose of IMP to the date of death or PD, whichever is earlier. For subjects whose BOR is PR or CR using RECIST v1.1, the date of first documented objective tumor progression or death that occurs after the last documented PR or CR, and prior to the start of post-treatment anti-cancer therapy will be used as the PFS event date. Subjects who die without a reported prior progression will be considered to have progressed on the date of their death. Subjects who remain alive and do not progress will be censored on the last tumor assessment date. Subjects who start subsequent therapy without a prior reported progression will be censored on the date of last tumor assessment prior to initiation of subsequent anticancer therapy. Subjects who have no post-baseline tumor assessments and do not die will be censored on Day 1.

The median PFS time, along with its two-sided 95% CI, will be estimated using the KM method. In addition, two-sided 95% CIs for the PFS rate will be constructed at pre-specified time intervals (such as 3 months, 6 months, ..., etc.), using the log-log transformation methodology of Kalbfleisch and Prentice (Kalbfleisch, 1980) where the estimated variance of $\log(-\log(\hat{S}(t)))$ is:

$$\tau^2(t) = \sigma^2 [\hat{S}(t) \log(\hat{S}(t))]^2$$

The 100 x (1- α)% CI for S(t) is given by:

$$\left[\hat{S}(t) \right]^{\exp(z_{\alpha/2} \tau(t))} \leq S(t) \leq \left[\hat{S}(t) \right]^{\exp(-z_{\alpha/2} \tau(t))}$$

Overall Survival (OS)

Overall survival is defined as the time from the first dose of IMP to the date of death due to any cause. For subjects who do not die, the OS time will be censored on the date when the subject was last known to be alive. The date “last known to be alive” will be defined as the latest date of contact with the subject based on the following: non-imputed AE start and stop dates, visit/collection dates (including unscheduled visits) of pharmacokinetic/pharmacodynamic/Biomarker/ADA assessments, serum/urine pregnancy tests, safety laboratory collection (i.e., hematology, serum chemistry, coagulation profiles, thyroid function, and urinalysis), vital signs, pulse oximetry, physical exams, ECG assessments, tumor biopsy or tumor assessments, concomitant medication/post treatment

cancer therapy, and extended survival follow-up contact dates where the subject's status is "alive". The analysis methodology for OS will be similar to that used for PFS.

